9.7.5 Prevalence of immunology testing

- The following summaries will be performed: Number (and %) of patients with any immunology testing among Group 1 and 2 respectively, including 95% confidence interval for the percent for the respective group. The confidence interval will be calculated based on normal approximation for the proportions (exact method may be used if sample size is too small).
- Number (and %) for type of immunology testing performed (alglucosidase alfa IgE, alglucosidase alfa IgG, complement activation, or serum tryptase) within Group 1 and 2 respectively.
- Subgroup analysis as determined by the following covariates:
 - by age group (<18 years and >=18 years respectively)
 - by gender (male, female)
 - by country (or region if sample size is small for certain regions)

In addition, the difference in prevalence rate between two groups will be calculated, with corresponding 95% confidence interval calculated based on normal approximation of two proportions. Exact confidence interval may be used if sample size is too small.

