9.5 STUDY SIZE

All patients available in the study population will be considered for the analysis.

No assumption will be made on the expected number of patients with spontaneously reported significant hypersensitivity/anaphylactic reaction occurring during alglucosidase alfa treatment course in countries in Europe.

The Table 3 provides expected precision (95% confidence intervals) according to different values of expected prevalence of immunology testing. The expected value of prevalence is not known and a range of potential values is presented in the table below.

Table 3 - 95% confidence intervals according to different values of prevalence of immunology testing

	Prevalence				
Number of patients	50%	75%	85%	90%	95%
50	[35.5- 64.5%] ^a	[60.7-86.2%] ^a	[72.1-93.5%] ^a	[78.2-96.7%] ^a	[84.8-99.1%] ^a
100	[40.2-59.8%]	[66.5-83.5%]	[78.0-92.0%]	[84.1-95.9%]	[90.7-99.3%]
200	[43.1-56.9%]	[69.0-81.0%]	[80.1-89.9%]	[85.8-94.2%]	[92.0-98.0%]
300	[44.3-55.7%]	[70.1-79.9%]	[81.0-89.0%]	[86.6-93.4%]	[92.5-97.5%]

a Exact 95% confidence interval using binomial exact method (Clopper-Pearson exact method)

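### The switch from normal-approximation to exact intervals depends on sample size alone, so it misses the high prevalences where the approximation falls short of 95% coverage

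*Protocol*

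**What the plan says.** Protocol section 9.7.5 plans, for each of the two periods, the number and percentage of patients with any immunology test, "including 95% confidence interval for the percent for the respective group". The method for that interval is: "The confidence interval will be calculated based on normal approximation for the proportions (exact method may be used if sample size is too small").

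For the difference between periods, the same section plans an estimate "with corresponding 95% confidence interval calculated based on normal approximation of two proportions", followed by: "Exact confidence interval may be used if sample size is too small".

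Section 9.5 commits to no patient number ("No assumption will be made on the expected number of patients with spontaneously reported significant hypersensitivity/anaphylactic reaction") and no prevalence ("The expected value of prevalence is not known and a range of potential values is presented in the table below"). Table 3 runs over 50, 100, 200 and 300 patients and over prevalences of 50, 75, 85, 90 and 95%. Only the 50-patient row carries the footnote "Exact 95% confidence interval using binomial exact method (Clopper-Pearson exact method").

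Sections 4 and 12 plan a first interim report with one post-implementation year set against the full three-year pre-implementation period. Section 9.7 calls the analyses descriptive.

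**The concern.** The accuracy of a normal-approximation (Wald) interval for a proportion depends on the smaller of the two expected counts. Here that is the number of untested patients, n(1 − p), when prevalence p is high. A rule that looks at n alone cannot detect that 100 patients at 95% prevalence leave only 5 expected untested. The rule also has no numeric threshold and is permissive, so the method could be chosen after the data are seen.

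At high prevalence the Wald interval is too narrow and sits too high, so its lower limit overstates how many patients can be said to be tested. There is no test or success margin, so the intervals carry all the statements of uncertainty that go to the regulator.

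**Working it through.** **Inputs.** The confidence level is 95% (z = 1.96), and the grid of n and prevalence is that of Table 3 (section 9.5). The default method is from section 9.7.5. The interim group sizes are an assumption, since the protocol gives none: 100 pre and 33 post, that is, one post year out of three at equal yearly numbers.

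**Step 1: reproduce Table 3.** Wald limits are p ± 1.96·√(p(1 − p)/n). For n = 100 and p = 0.95: √(0.95 × 0.05/100) = 0.0218; 1.96 × 0.0218 = 0.0427; limits 90.7% and 99.3%, as printed. All 15 cells for n = 100, 200 and 300 match Wald to 0.1 point. The n = 50 row matches Clopper-Pearson, apart from one last digit (99.2% computed, 99.1% printed).

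**Step 2: the same cell by other methods.** For 95 tested out of 100:

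| Method | 95% interval |
|---|---|
| Wald (Table 3) | 90.7-99.3% |
| Clopper-Pearson | 88.7-98.4% |
| Wilson | 88.8-97.8% |

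The printed lower limit is about 2 points higher than either alternative.

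**Step 3: coverage of a single prevalence.** Coverage is the sum of the binomial probabilities P(X = x) over all x whose interval contains p. For n = 100 and p = 0.95, the Wald interval contains 95% only for x = 89 to 97. The probability of x ≥ 98 is 11.8% (lower limit above the truth; nominal 2.5%) and of x ≤ 88 is 0.4%. The remainder is 87.7%.

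Wald coverage (%) over the grid of Table 3:

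| n | 50% | 75% | 85% | 90% | 95% |
|---|---|---|---|---|---|
| 50 | 93.5 | 94.1 | 94.1 | 87.9 | 92.0 |
| 100 | 94.3 | 94.6 | 93.3 | 93.2 | 87.7 |
| 200 | 94.4 | 93.7 | 94.4 | 92.7 | 92.6 |
| 300 | 94.3 | 94.5 | 94.2 | 93.8 | 92.6 |

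At 50-85% the largest shortfall is 95 − 93.3 = 1.7 points. At 95% prevalence the expected untested counts are 100 × 0.05 = 5, 200 × 0.05 = 10 and 300 × 0.05 = 15, and coverage is still 92.6% at the last two. On the same grid Wilson covers 93.3-97.0% and Clopper-Pearson 95.4-98.8%. At n = 100 and 95% they give 96.6% and 98.3%.

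**Step 4: coverage of the difference.** The same sum runs over both binomials. The Wald half-width is 1.96·√(p₁(1 − p₁)/n₁ + p₂(1 − p₂)/n₂).

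| Groups | Prevalences | Wald | Newcombe |
|---|---|---|---|
| 50 vs 50 | equal, 50-95% | 94.1-94.6% | 94.3-97.9% |
| 100 vs 100 | equal, 50-95% | 94.4-94.9% | 94.4-96.4% |
| 100 vs 33 (assumed) | 90% / 90% | 92.3% | 95.8% |
| 100 vs 33 (assumed) | 95% / 95% | 85.7% | 96.5% |

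**Step 5: effect of mixing methods in Table 3.** At 95% prevalence the printed widths are 99.1 − 84.8 = 14.3 points (n = 50, exact) and 99.3 − 90.7 = 8.6 (n = 100, Wald), an apparent gain of 5.7. With the exact method in both rows the second width is 98.4 − 88.7 = 9.7 and the gain is 4.6.

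**The case against.** Several stronger readings are tempting, and the protocol does not support them.

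- **That the plan would report Wald intervals at 50 patients or fewer.** Table 3 uses Clopper-Pearson throughout its 50-patient row, and section 9.7.5 allows an exact method for small samples. Poor Wald coverage at such sizes therefore does not show what the plan would report, although section 9.7.5 does not commit to the switch.
- **That subgroup intervals will fail or collapse to zero width.** The subgroup bullet in section 9.7.5 names no interval and allows pooling of countries into regions.
- **That the effectiveness measure itself is unreliable.** Section 8 makes this the between-period difference, and with equal groups of 50 or more its Wald interval is adequate. At 100 against 67, a plausible second interim, coverage is 94.3-94.8% for equal prevalences of 50-95%. At 100 against 33 it is 93.4-94.1% for equal prevalences of 50-85%. The 85.7% needs both an assumed split and 95% prevalence in both periods.
- **That Table 3 is in error for not showing the difference.** A descriptive study with no size target need not tabulate it. The mixture of methods is disclosed by footnote and changes the apparent gain by only about 1 point.

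It is also fair to say that 100 patients at 95% is a low point of an oscillating curve: Wald coverage at n = 100 is 93.7% at a prevalence of 94% and 90.6% at 96%. But averaged over 92.5-97.5% it is still only 90.3% at n = 100, so the shortfall is not an artefact of one value.

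Finally, a numeric threshold could be left to a statistical analysis plan. That does not settle the matter, because the protocol already states both the default and its trigger, and the trigger uses the wrong quantity.

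**Conclusion.** The point holds within limits. The default and its size-only, optional fallback leave single-period intervals short of 95% coverage at high prevalence, even with samples that few would call small: 87.7% at 100 patients and 92.6% at 200 and 300 when prevalence is 95%. The misses fall mostly on the side that overstates testing. For the difference, a material loss arises only with unequal groups at high prevalence.

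The single-period result assumes only that true prevalence may reach 90-95%, values that the protocol itself tabulates and does not rule out. The interim result also rests on the assumed 100 against 33 patients. Importance is modest: the analysis is descriptive, with no test, margin or decision threshold.

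**What to change.** In section 9.7.5, name one method for all sample sizes and all reports:

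- **Each prevalence:** Wilson, or Clopper-Pearson, which Table 3 already names and which is more conservative.
- **Difference between periods:** Newcombe's hybrid-score interval, or Miettinen-Nurminen.

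Delete both permissive clauses ("exact method may be used if sample size is too small" and "Exact confidence interval may be used if sample size is too small"), so that no choice of method remains once the data are seen. Make the same change to the interval sentence in the synopsis. Recompute every row of Table 3 by the method chosen for a single prevalence.

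The cost is a wording change, one recomputed table and standard software options. Some intervals become slightly less favourable; for example, the lower limit for 95 tested out of 100 moves from 90.7% to 88.8% (Wilson) or 88.7% (Clopper-Pearson).

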9.2 SETTING

The following data sources will be considered:

- Genzyme's Pharmacovigilance adverse event database,
- Genzyme Clinical Specialty Laboratory database (capturing records and results of immunology testing conducted in these laboratories).

Reports pertaining to the same patients will be linked across databases using date of birth, initials and country of origin.

The Genzyme's Pharmacovigilance adverse event database will be used to identify the population of interest for each study period:

• All patients with a spontaneously reported significant hypersensitivity/anaphylactic reaction occurring during alglucosidase alfa treatment course in countries in Europe.

The following criteria will be used to identify patients with a reported significant hypersensitivity/anaphylactic reaction occurring during alglucosidase alfa treatment course:

• cases identified by the Standardized MedDRA Query "Anaphylactic reaction" and "hypersensitivity".

The Genzyme Clinical Specialty Laboratory database will be used to identify the full history of immunology testing since initiation of treatment with alglucosidase alfa in patients identified from the Genzyme's Pharmacovigilance adverse event database.

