9.7 DATA ANALYSIS

The analyses will be descriptive and will be made on all patients available in the databases at time of each analysis.

9.7.1 Analysis population:

The primary analysis population will be patients with spontaneously reported significant hypersensitivity/anaphylactic reaction while treated with alglucosidase alfa treatment course in countries in Europe. Patients will be divided by following two groups:

Group 1 (pre-SIP):

- Patients with hypersensitivity/anaphylactic reaction event onset date from 01 September 2012 to 31 August 2015

Group 2 (post-SIP):

 Patients with hypersensitivity/anaphylactic reaction event onset date from 01 October 2015 to 30 September 2018

9.7.2 Determination of patient status on immunology testing:

A patient in Group 1 (or 2) will be considered having undergone any immunology testing (immunology test = Yes) for the respectively period if one of the two conditions is met:

- i) a valid test result is available for at least one of the following tests from Genzyme Clinical Specialty Laboratory database
 - a. alglucosidase alfa IgE antibody,
 - b. alglucosidase alfa IgG antibody,
 - c. complement activation,
 - d. serum tryptase
- ii) the test date is after the alglucosidase alfa treatment start date through the end of the period cutoff (31 August 2015 for Group 1 and 30 September 2018 for Group 2)

Note that patients without a valid test meeting above criteria will be considered without having immunology test performed (immunology test=No). Therefore, there is no missing data for this endpoint.

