9.7.3 Demographic and baseline disease characteristics

Patient demographics and baseline disease characteristics will be summarized using descriptive statistics: number of observations (n), mean, median, standard deviation (SD), minimum, and maximum. Categorical variables will be summarized using frequencies and percentages. Denominator will be based on the number of patients in the analysis population as defined in Section 9.7.1.

Following variables will be summarized by Group (1 or 2):

- patient characteristics (age, gender, weight, country/region)
- history of hypersensitivity/anaphylactic reactions

9.7.4 Alglucosidase alfa treatment information and the details on hypersensitivity/anaphylactic reaction event

Following alglucosidase alfa treatment information will be summarized by group as well as the combined analysis population:

- time from treatment initiation to first onset of hypersensitivity/anaphylactic reactions event within the study period
- number of doses received prior to first onset of hypersensitivity/anaphylactic reactions event within the period

The details of the hypersensitivity/anaphylactic reactions event reported in each of the periods will be summarized by intensity, seriousness (SAE or not) of the event, and relationship to alglucosidase alfa treatment, respectively. The summaries will be provided by analysis group (1 and 2). For multiple events occurred in the same study period, patients will be counted only once and only the event with the worst category will be considered for the corresponding

analysis. Corresponding listing will be provided with detailed information collected in the database

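### A patient with reactions in both periods belongs to both groups, but the planned interval for the difference treats the groups as independent; with overlap it is too wide

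*Protocol*

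**What the plan says.** Section 9.7.1 of the protocol introduces the groups with "Patients will be divided by following two groups" and defines them by two onset windows. Group 1 is "Patients with hypersensitivity/anaphylactic reaction event onset date from 01 September 2012 to 31 August 2015" and Group 2 is "Patients with hypersensitivity/anaphylactic reaction event onset date from 01 October 2015 to 30 September 2018". There is no rule for a patient who has an event in each window.

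The only counting rule is in section 9.7.4: "For multiple events occurred in the same study period, patients will be counted only once". It works within a period and is written for the summaries of event details.

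Section 9.7.2 counts a test when "the test date is after the alglucosidase alfa treatment start date through the end of the period cutoff". Section 9.2 likewise takes the "full history of immunology testing since initiation of treatment with alglucosidase alfa". The two conditions in 9.7.2 are joined by "if one of the two conditions is met", although the note that follows them reads as if both were needed.

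For the comparison, section 9.7.5 states that "the difference in prevalence rate between two groups will be calculated, with corresponding 95% confidence interval calculated based on normal approximation of two proportions", with an exact interval as the fallback in small samples. Section 9.9 does not list shared patients as a limitation.

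**The concern.** The two windows are only one month apart. The protocol itself expects recurrence: it provides for several events per patient and summarises the history of earlier reactions. Some patients may well meet both group definitions.

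A normal-approximation interval for two proportions adds the two variances and has no term for patients who contribute to both. The exact fallback, in its usual two-sample form, makes the same assumption. If patients are shared, the reported 95% interval does not have 95% coverage. It is attached to the one comparison that section 8 uses to judge whether the revised safety information packet worked.

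**Working it through.** **The plan's own figures.** Table 3 (section 9.5) is the only computed precision in the protocol, and it concerns a single prevalence. With p ± 1.96·√(p(1−p)/n), n = 100 and p = 50% give 50 ± 9.8, i.e. 40.2 to 59.8; p = 75% gives 66.5 to 83.5. Both match. Over the whole table, 19 of 20 cells match to 0.1 point. The exception is the upper limit at n = 50 and 95% (99.2 computed, 99.1 stated), where the implied count of 47.5 is not a whole number. The protocol gives no figure for the difference or for the overlap.

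**Inputs.** Group sizes and prevalences are taken from the grid of Table 3. The overlap is an assumption, varied from 0 to 50% of each group. Shared patients are assumed to have the same prevalences as the rest of their group.

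**Covariance.** Let m patients be in both groups, with prevalences p1 and p2 among them. For one patient the Group 2 test window contains the Group 1 window, so Yes in Group 1 implies Yes in Group 2. Then P(Yes in both) = p1, and the covariance per patient is p1 − p1·p2 = p1(1−p2) ≥ 0. For the two group proportions:

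- Planned variance: V = p1(1−p1)/n1 + p2(1−p2)/n2
- Covariance: C = m·p1(1−p2)/(n1·n2)
- Correct variance: V − 2C

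If condition i) of 9.7.2 alone is enough, a shared patient has the same status in both groups. The covariance per patient is then p(1−p), with p the common prevalence, again not negative.

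**Numbers for n = 100 per group, 50% vs 75%.** V = 0.0025 + 0.001875 = 0.004375, so the planned half-width is 1.96·√0.004375 = 13.0 points. At 30% overlap, C = 30·0.5·0.25/10,000 = 0.000375 and V − 2C = 0.003625, so the correct half-width is 11.8 points.

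| Overlap (assumed) | Correct half-width, 50% vs 75% (planned 13.0) | Actual coverage, 50% vs 75% | Correct half-width, 75% vs 85% (planned 11.0) |
|---|---|---|---|
| 0% | 13.0 | 95.0% | 11.0 |
| 10% | 12.6 | 95.6% | 10.6 |
| 30% | 11.8 | 96.9% | 9.8 |
| 50% | 11.0 | 98.0% | 8.8 |

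From 10% to 50% overlap, the planned interval is 3% to 18% too wide in the first case and 4% to 25% in the second. A simulation of the 50% vs 75% case gave coverage of 94.8%, 96.7% and 97.9% at 0%, 30% and 50% overlap, in line with the formula.

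**Effect on the difference itself**, with 30 shared patients and assumed rates:

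- n = 100/100, others 50%/50%, shared 50% to 65%: Group 2 = (70·0.50 + 30·0.65)/100 = 54.5%. The difference is +4.5 points, against 0 in the others.
- n = 100/100, others 50%/75%, shared 90% to 95%: 62% and 81%. The difference is 19 points, against 25.
- n1 = 75, n2 = 150, others 60%/60%, shared 90% to 95%: (27 + 27)/75 = 72% and (72 + 28.5)/150 = 67%. The difference is −5 points, against 0.

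**The case against.** The strongest reply has four parts.

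- **The groups may be meant to be disjoint.** The word used in 9.7.1 can be read that way. No rule carries it out, however: the definitions admit a patient to both groups, and nothing says which group would take precedence.
- **The error is on the safe side, and the analysis is declared descriptive.** This stands as a limit on the weight of the point. At 10% overlap the half-width changes by only 0.4 points. But a reported 95% interval should have its stated coverage, and precision that may already be poor should not be given away.
- **The size depends on an overlap that the documents do not give.** This also stands. The figures are illustrations over a range, and the error is nil if nobody is shared.
- **Such detail belongs in a statistical analysis plan.** Here the protocol itself fixes the group definitions, the testing status and the interval method, and the three do not fit together.

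A reader might go further and infer that, because status never moves from Yes to No, shared patients can only add to the apparent effect. The documents do not support that. The statement is true of a shared patient's own status. The crude difference, though, also depends on how shared patients compare with the others and on the group sizes, and the examples show it raised, diluted and reversed. Nor can every later first test in a shared patient be called spurious: a test prompted by the revised packet is what the study sets out to detect, and the documents give no split between the two kinds.

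**Conclusion.** The point holds for the interval. Under the current definitions a patient can be in both groups, and the method in 9.7.5 ignores the resulting positive covariance. The planned interval is then too wide: at n = 100 per group and 50% vs 75%, by 0.4 points of half-width at 10% overlap and by 2.0 points at 50%. This rests on an assumed overlap and on similar prevalences in shared and other patients. The sign of the error holds under either reading of the conditions in 9.7.2. No fixed direction of bias in the estimated difference is claimed.

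**What to change.** In section 9.7.5, compute the interval for the difference with a variance that accounts for patients in both groups: the covariance term above, a patient-clustered robust variance, or a bootstrap that resamples patients. A covariance estimated from the data serves under either reading of 9.7.2. Report how many patients are in both groups. Add a sensitivity analysis that counts each patient once, in the period of the first study reaction. It belongs as a sensitivity analysis because it removes from Group 2 everyone who also reacted in the earlier period.

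The cost is a few lines of code, since reports are already to be linked by patient, and a method slightly less simple to describe. Whether tests done before the reaction should count at all is a separate question, which also touches Group 2 patients with no earlier reaction. It is not part of this change.

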9.8 QUALITY CONTROL

This study will be conducted according to sanofi operational quality standards for analyses of pre-existing data (QOQS-009473) and Statistical activities (QOQS-006704) as well as standard operating procedure for GPE epidemiologic studies (QSOP-001126). Full list of quality documents is provided in Annex 1.

Linkage between Genzyme's Pharmacovigilance adverse event database and clinical specialty laboratory database, as well as the QC process will be described and documented as part of the study file including description of manual checks of all available data sources.

Statistical deliverables as well any data derivation or transformation will be quality controlled according to Sanofi standard operating procedure (QSOP-002240). The method and type of quality control performed for TLFs will be detailed in a Quality Control plan for this study.

